Our study period will extend 11 years (January 2004 to December 2014), a period of rapid growth of HDHPs,²² capturing an unprecedented sample size of patients with bipolar disorder transitioning to HDHPs. The intervention cohorts will include individuals who transitioned to HDHPs between January 2005 (after a minimum one year baseline period in a traditional plan) and December 2013 (to allow one year of follow-up). We will follow all subjects for 1 year before and 1 year after the index month of switching (*Figure 3*). Matched controls will be drawn from employers who chose to remain in a traditional plan in the same calendar year, and our matching approach will ensure calendar month of switch is also balanced across the study groups. We will require continuous enrollment for the 24 month study period for both groups.

Figure 3. Study design of HDHP members and controls

* A subgroup of members are “forced switchers” whose employers mandate that they transition from a traditional to a high-deductible health plan

C.5 Study Population for Aims 1-3 [RQ-3; CI-1 to CI-4; HT-1 to HT-4]: Inclusion Criteria: We will include health plan members aged 12 to 64 years at the beginning of the baseline period. Consistent with prior research,⁸⁹⁻⁹¹ we will use medical claims data and a validated algorithm^{36,41,43-45,92,93} to identify members who had at least two ambulatory encounters or one hospital encounter with a diagnosis of bipolar disorder (ICD-9 diagnostic codes: bipolar-I: 296.0, 296.1, 296.4-296.7; bipolar-II: 296.89; and bipolar-other: 301.11 and 301.13^{43-45,89-91}). The first advisory panel committee meeting in October 2015 directly shaped our cohort definition stream of work; advisors agreed that bipolar inclusion criteria should include requiring at least 1 inpatient or 2 outpatient diagnoses, to better ensure that the diagnosis is valid and relevant to the planned analyses. Despite the tightening of our diagnostic criteria, our newest cohort totals remain on target with the estimates in our original power analysis. Eligibility for the study is predicated on the principal diagnosis of bipolar disorder (any diagnosis) not just diagnosis at the first position, as advised by our stakeholder panel. The study cohort was derived through applying the following inclusion rules, therefore defining individuals as eligible for our study:

[name]

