Study cohort: Of 41,638,597 members enrolled in the national insurer during 2004-2012, we found 18,184,556 have a 2-year enrollment span, a study inclusion criterion. Among these, 148,706 have at least 1 inpatient or 2 outpatient diagnoses of bipolar disorder; this reflects a prevalence of 1% members with bipolar disorder, which is consistent with expectation among the commercially insured population. Among 148,706 members with bipolar disorder, 57,028 matched our age criterion (12 to 64 years of age). (We will conduct sensitivity analyses of our main results varying our bipolar diagnosis criteria [e.g., requiring diagnosis prior to index date, requiring only one diagnosis; [CI-5](#)]) To minimize selection bias, our study cohorts will include individuals whose employers offer only a single benefit type with no choice. Our intervention cohorts will include traditional plan members with bipolar illness who experience an employer-mandated switch to HSA-eligible HDHPs with full drug cost-sharing (i.e., out-of-pocket medications payments until the deductible limit is reached), or to HSA-ineligible HDHPs that subject medications only to copayments as in traditional health plans. The control cohort will include members with bipolar illness whose employers offered only a traditional plan for the follow-up year. We estimate that 7,227 have HDHP insurance and 49,801 have traditional plan insurance. **Exclusion Criteria:** We will exclude members age 65 years or older who could be eligible for Medicare benefits, including drug coverage through Medicare Part D. We will also exclude members whose employer offered a choice of health plan. This strengthens our design by reducing potential selection bias due to, for example, healthier members selecting HDHPs or individuals anticipating discretionary utilization. . Input from our panel advisory meetings led to the decision to exclude from our cohort those individuals with a diagnosis of schizoaffective disorder or schizophrenia in order to identify a clinically homogenous group for our study, as advised by our clinical psychiatrist co-investigator [name]. This criterion was further supported by our advisors at DBSA. According to sources at DBSA, schizophrenia and schizoaffective disorder are not comorbidities seen in their peer population. In their judgment, people living with schizophrenia and schizoaffective disorder are unlikely to come to DBSA meetings and would have their needs better met in other settings. The ineligibility criteria therefore included the 3 categories: 1) patients with only 1 outpatient bipolar diagnosis, 2) 1 inpatient or 2 outpatient diagnosis of schizophrenia diagnosis, and 3) 1 inpatient or 2 outpatient diagnosis of schizoaffective disorder. We estimate 3,731 individuals were excluded from the study cohort due to evidence of schizoaffective disorder and schizophrenia. There have been no changes in identifying eligible individuals to enroll in our approved research plan beyond the stakeholder advisory panel decision to exclude schizoaffective disorder and schizophrenia, calculate their overlap with the bipolar population, and exclude them from the final cohort.

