C.10 Sample Size Estimates and Power Calculations [HT-1 to HT-4]: Using 10 years of data (2003-2012), we found 42 million unique adolescents and adults aged 12-64, approximately 450,000 of whom (~1%) had at least one bipolar disorder diagnosis. This is consistent with our expectation of a lower disease prevalence among commercially-insured adults compared with the 3% prevalence estimated by epidemiological surveys,³ because individuals with bipolar disorder less commonly have private insurance.¹³¹ A total of 109,012 of the 450,000 with a bipolar diagnosis met our inclusion criteria of 2 years continuous enrollment, with the first year in a traditional plan, the second in a traditional or HDHP, and no choice from the employer at any point regarding plan type. Projecting to 2014, our sample will include over 10,800 HDHP members (1525 HSA and 9275 non-HSA) and 43,200 matched traditional plan controls with bipolar illness (1:4 matching). Our smallest HDHP subgroups examined for primary outcomes will include 1525 HSA members (smallest medication adherence cohort) and 2160 non-white members (smallest emergency department and hospitalization outcome cohort).

For interrupted time series analyses of medication adherence, based on assumptions including 12 months of follow-up, autocorrelation of less than 0.3, and 0.05 type I error,¹³² we will have greater than 90% power to detect a 6% relative decrease in adherence in our smallest medication outcome subgroup (HSA-HDHP members). For example, we could detect an adherence rate change from 49% (as seen in previous literature¹³³) to 46% with a standard deviation of 1.5%. This is a *smaller* change in adherence than has been observed previously in HDHP-HSA studies.⁵⁷

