We will use generalized estimating equations to model difference-in-differences analyses of our least frequent outcomes, including emergency department visits and hospitalizations. Based on the smallest subgroup of 2160 non-white HDHP members and their 8640 matched traditional plan controls, a baseline psychiatric hospitalization rate of 10% per year,⁸⁹ (the lowest rate among our measures), 0.05 type I error, 80% power, and a conservative repeated observations correlation assumption of 1, we will be able to detect a 20% relative decrease (e.g., from 10% to 8%). This is smaller than the 27% hospitalization decline we detected in a previous HDHP study.⁵⁴ We will have more power to detect changes for all other outcomes. The power estimates were calculated using PASS software.¹³⁴

C.11 Study Population and Methods for Aim 4 [RQ-3; PC-2]: Ours will be the first qualitative study to explore views of patients with bipolar illness regarding insurance-related barriers to care and experiences with commercial insurance benefits. Qualitative results will complement and inform our quantitative claims-based analyses in Aims 1-3. For Aim 4, DBSA will assist in recruiting **individuals living with bipolar disorder or close family members** to participate in semi-structured telephone interviews. The opportunity to volunteer for participation in interviews will be presented in local DBSA chapter in the form of a flyer for attendees. These flyers will be distributed by DBSA to chapter leadership by means of US mail, email, and routine in-person outreach visits by DBSA officials to chapter meetings. Interested individuals who see the flyer will telephone our co-investigator [name] at DBSA in Chicago. [name] will conduct an initial screening for eligibility, focused on insurance coverage type, English competence, and achieving a rough US geographic balance. [name] will transmit contact details of individual interested in participating to the DPM/HPHCI team. We anticipate identifying ~100 candidate respondents at DBSA, to allow for drop-out due to additional screening, scheduling conflicts, non-consent, etc. In order to achieve full saturation of themes, we anticipate needing 40 completed interviews, as described below. We will schedule more interviews (~60 in total) in order to pilot test our instrument and to account for partial or non-informative interviews.

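### C.10's sample sizes and subgroup power rest on a one-diagnosis cohort that C.5 has replaced, so the claim that cohort totals are on target is not shown for the HDHP arm

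*Combined protocol and SAP*

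**What the plan says.** C.10 (Sample Size Estimates and Power Calculations) starts from 2003-2012 data with 42 million members aged 12-64, "approximately 450,000 of whom (~1%) had at least one bipolar disorder diagnosis". It continues: "A total of 109,012 of the 450,000 with a bipolar diagnosis met our inclusion criteria of 2 years continuous enrollment", together with the plan-sequence and no-choice conditions. From there: "Projecting to 2014, our sample will include over 10,800 HDHP members (1525 HSA and 9275 non-HSA", with 43,200 matched controls at 1:4. The difference-in-differences power is "Based on the smallest subgroup of 2160 non-white HDHP members and their 8640 matched traditional plan controls", a 10% baseline psychiatric hospitalization rate, 0.05 type I error and 80% power, giving a detectable 20% relative decrease.

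C.5 (Study Population for Aims 1-3) now requires one inpatient or two outpatient diagnoses. Its exclusion text reads: "The ineligibility criteria therefore included the 3 categories: 1) patients with only 1 outpatient bipolar diagnosis". Its study-cohort paragraph counts 57,028 people in 2004-2012 and adds: "We estimate that 7,227 have HDHP insurance and 49,801 have traditional plan insurance". It also reports: "We estimate 3,731 individuals were excluded from the study cohort due to evidence of schizoaffective disorder and schizophrenia". Of the tighter rule it says: "Despite the tightening of our diagnostic criteria, our newest cohort totals remain on target with the estimates in our original power analysis".

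B.2 and C.1 still describe about 109,000 patients, and F.3 well over 100,000, as the people who meet the study criteria.

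**The concern.** Two incompatible totals are presented as the study cohort, and the only power analysis in the document belongs to the one that C.5 no longer uses for the main analysis. The on-target sentence relies on that analysis as still valid, yet the counts that drive it (HDHP, HSA, non-white) have not been restated.

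This matters because effects in vulnerable subgroups are a declared purpose of the study, and B.2 claims the study is the first large enough to examine them. If power in non-white members is nearer 65-75% than 80%, a null result there could be misread as no effect.

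**Working it through.** **Cohort arithmetic**

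- C.5 split: 7,227 + 49,801 = 57,028, which is exact.
- Current against old eligible total: 57,028 / 109,012 = 52%.
- C.10's planned matched sample: 10,800 + 43,200 = 54,000. The 57,028 exceeds this, but it is an eligible pool and not a matched sample. At 1:4 the HDHP count is binding: 7,227 × 5 = 36,135.
- HDHP arm: 7,227 / 10,800 = 67%, with 7,227 covering 2004-2012 and 10,800 projected to 2014.

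**Reproducing C.10**

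Inputs from C.10: n = 2,160 HDHP, 4n = 8,640 controls, p1 = 0.08, p2 = 0.10, alpha 0.05. Two-sided testing is assumed, since sidedness is not stated. The repeated-observations correlation of 1 is read as one effective observation per person, so this is a pooled two-proportion test:

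power = Φ{ [ |p1 − p2| − 1.96 √( p̄(1 − p̄)(1/n + 1/4n) ) ] / √( p1(1 − p1)/n + p2(1 − p2)/4n ) }, with p̄ = (0.08 + 4 × 0.10)/5 = 0.096.

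At n = 2,160 this gives 82.0%, or 80.9% with continuity correction. The decrease detectable at 80% power is 19.5% relative, so the stated 20% reproduces. Exactly 80% power for 10% versus 8% takes 2,055 HDHP members (2,117 with correction).

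**The current cohort**

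Assumption: C.10's non-white share, 2,160 / 10,800 = 20%, still holds. The 7,227 is carried to the end of the study in two ways: from 7 to 9 index years (2005-2011 to 2005-2013), or from 8 to 10 two-year spans (2004-2012 to 2004-2014). Growth is either zero or 4^(1/8) − 1 = 18.9% a year, taken from the fourfold rise in national HDHP enrollment in 2006-2014 cited in A.3.

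- Flat: 7,227 × 9/7 = 9,292; 7,227 × 10/8 = 9,034.
- Growing (ratio of geometric sums): 11,487 and 11,218.

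| Case | HDHP | Non-white (20%) | Power, 10% vs 8% | Detectable relative decrease |
|---|---|---|---|---|
| C.10 as stated | 10,800 | 2,160 | 81-82% | 19.5% |
| Current, unprojected | 7,227 | 1,445 | 62-64% | about 24% |
| Current, flat switching | 9,034-9,292 | 1,807-1,858 | 73-76% | 21-22% |
| Current, 19% yearly growth | 11,218-11,487 | 2,244-2,297 | 82-84% | 19% |

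Power ranges run from with to without continuity correction, across both projections. Detectable decreases are without correction.

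**Growth at which C.10's figures are recovered.** At a 20% share, 80% power for 10% versus 8% corresponds to about 10,270-10,581 HDHP members, or 9-14% yearly growth. Reaching 10,800 takes 14-16%.

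**The 3,731 exclusions.** C.5 does not say whether they are already out of 57,028. If they are not, and they fall pro rata (assumption), the HDHP count is 7,227 × 53,297 / 57,028 = 6,754. The three current cases then become 59-61%, 70-73% and 80-82%.

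**Whole HDHP arm.** 7,227 against 28,908 controls gives over 99.9% power for 10% versus 8%.

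Power for the HSA time-series analysis was not recomputed, because no current HSA count is given.

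**The case against.** The strongest reply is that nothing is shown to be lost. The 7,227 stops at 2012, index dates run to December 2013, and C.4 calls the period one of rapid HDHP growth. The unprojected case is therefore not a plausible final sample. On the only growth rate in the document, power is at or above C.10's. That is fair, and it is why a shortfall cannot be asserted. But the rate is for national enrollment, not employer-mandated switching at this insurer, and the plan makes no projection of its own.

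C.10 also judges its 20% against a 27% hospitalization decline in an earlier HDHP study. Even the smallest count, 1,351 (20% of 6,754), has a detectable decrease of about 24.5%, below 27%, and about 87-88% power for a 27% decline. This stands and limits the consequence. It does not make the stated 20% correct for the current cohort.

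Three further points stand in part:

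- C.10 takes 2,160 as given and solves for the effect, so it has little slack by construction. 2,160 is not a recruitment requirement.
- The stricter rule probably keeps sicker patients. With a 12% baseline (an assumption), power for a 20% relative decrease at 1,807-1,858 would be 83-84%.
- The 52% ratio may mix filters, because C.5 does not make clear where the no-choice rule was applied. The 49,801 traditional members already exceed the 43,200 planned controls, so control supply is not the evident constraint.

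The one-diagnosis rule does survive as a sensitivity analysis, but that does not power the main one.

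**Conclusion.** The concern holds. C.10's counts and subgroup power, and the totals in B.2, C.1 and F.3, describe a superseded primary cohort, and the on-target statement is unsupported for the HDHP arm and its subgroups. The documents do not prove that the target is missed.

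For non-white members, projected power for 10% versus 8% runs from 73% to 84% depending on HDHP growth that the plan does not report, or from 70% to 82% if the 3,731 are still to be removed. This rests on a constant 20% non-white share, a 10% baseline and full 1:4 matching. The overall HDHP comparison is not threatened. The point should be corrected, but it does not undermine the design.

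**What to change.** 1. Recount through 2014 under the adopted diagnosis rule and all other criteria, including a no-choice employer and a first year in a traditional plan. State the order in which the filters apply and whether the 3,731 are already out of 57,028.
2. Replace the eligible, HDHP, HSA, non-HSA, non-white and control counts in B.2, C.1, C.10 and F.3.
3. Rerun C.10 on those counts, including the HSA adherence calculation. Restate power or detectable effects and the control ratio that matching can achieve.
4. Keep, revise or delete the on-target sentence according to the recount.

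The cost is minor: a recount of data that will be in-house and a rerun of the power calculations. The stated subgroup power may come out less favourable.

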We will use a range of analytical methods tailored to our study outcomes. Specifically, we will use two strong quasi-experimental, longitudinal research designs: an **interrupted time series with comparison series design** and a **pre-post with propensity-matched comparison group difference-in-differences design**. The Cochrane Collaboration (an independent organization that produces and disseminates systematic reviews of health care interventions) considers both to be strong research designs that permit causal inference.^{80,81} Moreover, we will use a range of statistical methods including generalized linear mixed models,^{82,83} and interrupted aggregate and patient-level time series models^{58,84} as appropriate for each of our study outcomes. Study design features that strengthen the internal validity of the proposed research and reduce member- and employer-level selection biases include (i) selecting only employers that offer only one health plan type to employees, (ii) using a validated two-level (employer and member) **propensity score matching approach**,^{77,85} and (iii) propensity score matching on baseline population characteristics, including the functional form of the baseline outcome trends.⁷⁷ Cutting-edge research has shown that this matching approach leads to effect estimates that closely approximate randomized controlled trials.⁷⁷ These approaches will reduce baseline differences between employers choosing among the three possible types of insurance and control for potential patient-level differences in employee populations.

In **Aim 4**, we will conduct in-depth interviews with approximately 40 commercially insured individuals with bipolar disorder or their family caregivers to explore how they navigate deductibles, copayments, and other complex insurance features. We will also determine the health care services that patients most value and assess how they prioritize difficult health care cost tradeoffs.

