Employer-level Propensity Matching: The study population will include employees of firms that mandated a switch to HDHPs and others that kept traditional plans as their sole insurance option. While this minimizes member-level selection into health plans, our previous work indicates that some employers might select HDHPs based on employee characteristics.¹⁰⁰ To create strata of employers with similar baseline characteristics, we will generate scores predicting the propensity of an employer switching to an HDHP in a given year among all employers making such a decision. Propensity scoring is a well-established method that assists in generating a comparison group with a similar likelihood of being exposed to a given “intervention” (in this case, shifting to HDHP coverage) based on measured characteristics when subjects have not been randomly allocated into study groups.¹⁰¹⁻¹⁰⁴ We will use logistic regression to predict an employer’s likelihood of switching to an HDHP (versus remaining in a traditional plan). Candidate predictors in our propensity score models will include baseline employer-level covariates (Section C.8). We will use results from this model to divide employers into four strata according to propensity score, then match HDHP members with bipolar illness to traditional plan members with bipolar illness within each stratum (see immediately below).¹⁰⁴

Individual-level Propensity Matching: To identify closely matched patient controls for each of our HDHP study members with bipolar illness, we will use member-level propensity score matching¹⁰¹ to select members within the eligible pool of employees from each stratum of matched employers. Based on individual-level covariates (Section C.8) and similar enrollment dates, we will match four contemporaneous controls with bipolar disorder to each HDHP member with bipolar disorder within a pre-defined propensity score caliper (0.6 of the standard deviation of the pooled baseline propensity score).¹⁰⁵

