C.9 Analysis Plan for Aims 1-3 [IR-3; HT-1 to HT-4]: Overview: These analyses will determine how specific outcomes change after employer-mandated switching from traditional plans to HDHPs. To address methodological standard IR-3, we plan to use the most rigorous quasi-experimental retrospective longitudinal designs and analyses available for AIMS 1-3, namely interrupted time series with comparison series matched on multiple baseline covariates as well as the baseline trend of outcome measures. For Aim 4 we will use appropriate standard techniques for qualitative analyses of interview data (detailed below). We will first compare the characteristics of our matched cohorts (HSA-eligible and HSA-ineligible HDHP members, and traditional plan controls) using chi-square tests, t-tests and Poisson or quantile regression.¹²⁶ We will contrast sociodemographic characteristics, employer characteristics, and baseline health care utilization. Subsequent analyses will use time-series plots and rigorous analytical methods appropriate for each outcome, described below. Data collected on the same individuals in successive years are correlated (“repeated observations”). The extended general linear models—generalized estimating equations (GEE) and generalized linear mixed models (GLMM) for binary, count, or continuous measured outcomes—are appropriate methods for estimating parameters to adjust for these correlations within subjects.^{82,83} The term of interest in our GEE or GLMM models will be the interaction between *time* (pre versus post) and *cohort* (HDHP versus traditional plan). Statistical analyses in Aims 1-3 will first compare those transitioning to HDHPs with patients remaining in traditional plans; then contrast effects between HDHP members with full drug cost-sharing (HSA-eligible plans) and those transitioning to HDHPs without full drug cost-sharing (HSA-ineligible HDHPs). Each HDHP group will have as controls only those traditional plan members paired to a given HDHP member during the propensity score match. To examine possible selection effects due to applying our enrollment criteria and propensity matching approaches (see C.10), we will also compare our analytic population to members with bipolar disorder who were excluded from the sample.^[MD-4; CI-2]

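### One pooled HDHP-versus-traditional propensity score serves effects by HDHP type, so balance within the HSA arm is not assured and no step balances HSA against non-HSA members

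*Combined protocol and SAP*

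**What the plan says.** Section C.6 fits a logistic regression for an employer's "likelihood of switching to an HDHP (versus remaining in a traditional plan". It uses the result to "divide employers into four strata according to propensity score". Within those strata, "we will match four contemporaneous controls with bipolar disorder to each HDHP member with bipolar disorder", with a caliper of "0.6 of the standard deviation of the pooled baseline propensity score". HSA eligibility plays no part in either step. The binary outcome is explicit for the employer model. For the member score it is inferred, because the text speaks only of HDHP members and traditional plan members.

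Section C.9 first compares all HDHP members with traditional members, then contrasts the effects in HSA-eligible and HSA-ineligible plans. On controls it says: "Each HDHP group will have as controls only those traditional plan members paired to a given HDHP member during the propensity score match". Section C.1 says of the design features as a whole: "These approaches will reduce baseline differences between employers choosing among the three possible types of insurance". Section C.10 projects the sizes: "our sample will include over 10,800 HDHP members (1525 HSA and 9275 non-HSA) and 43,200 matched traditional plan controls".

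Several safeguards are also stated. The individual match includes the baseline outcome (C.6) and its trend (C.1, C.9). The Aim 1 and Aim 2 models adjust for patient-level covariates (C.9). A baseline comparison of the three cohorts is planned (C.9, and Section D under months 7-12).

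**The concern.** A propensity score balances covariates for the contrast it models. A score for any HDHP balances the pooled HDHP group against its controls. It does not by itself balance one type of HDHP. Two people with the same chance of entering some HDHP can have different chances of entering an HSA plan, and the covariates behind that difference are left free. About 86% of HDHP members are non-HSA, so the score mostly reflects selection into non-HSA plans.

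The contrast by type matters. Section B.2 presents the comparison of plans that do and do not place drugs under the deductible as new, and Section B.3 links it to possible changes in HSA law. If HSA and non-HSA employers or members differ, part of an apparent effect of drug cost-sharing could come from those differences.

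**Working it through.** **Plan figures.** 1525 + 9275 = 10,800 HDHP members, and 4 × 10,800 = 43,200 controls. Both agree with C.10. The HSA share is 1525/10,800 = 14.1%, with up to 4 × 1525 = 6100 controls.

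**When a pooled score is enough.** Let P(H|x) and P(N|x) be the chances of an HSA and a non-HSA plan given covariates x. The pooled score is e(x) = P(H|x) + P(N|x). Matching on e balances the pooled group. It also balances the HSA subset if P(H|x)/e(x) does not vary with x among people who share the same e. The documents give nothing by which to judge this.

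**Simulation 1.** Sizes are from C.10, with 1:4 greedy matching without replacement and a 0.6 SD caliper. Assumed: 80,000 potential controls and two standard normal covariates, with means shifted from controls as shown. Each row is a single draw. Cells give mean differences in SD units for the two covariates; HSA members are compared with their own retained controls.

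| HSA shift; non-HSA shift | Pooled HDHP vs controls | HSA vs own controls, pooled score | HSA vs controls, HSA-specific score |
|---|---|---|---|
| (0, 0); (0, 0) | -0.002, 0.002 | 0.012, -0.012 | -0.006, 0.003 |
| (0.3, 0.3); (0.3, 0.3) | 0.000, 0.003 | -0.002, 0.006 | 0.001, -0.001 |
| (0.2, 0); (0, 0.2) | -0.002, 0.000 | 0.197, -0.025 | 0.000, 0.010 |
| (0.3, -0.1); (0.1, 0.2) | 0.000, 0.000 | 0.242, -0.196 | 0.002, 0.005 |
| (0.5, -0.3); (0.1, 0.3) | 0.000, 0.000 | 0.459, -0.332 | 0.005, 0.004 |
| (0.5, 0); (0, 0.5) | 0.001, 0.002 | 0.496, -0.076 | 0.000, 0.026 |

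**Why pooled balance can hide this.** The pooled difference is 0.141 × (HSA difference) + 0.859 × (non-HSA difference). In the fourth row the non-HSA difference on the first covariate was -0.040, so 0.141 × 0.242 + 0.859 × (-0.040) = 0.034 - 0.034 = 0.

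**Simulation 2.** The pool is from C.5: 7,227 + 49,801 = 57,028 members, with HDHP split in the C.10 ratio into 1,020 HSA and 6,207 non-HSA. Plan choice depends on two covariates with assumed log-odds per SD. The HSA-versus-own-controls differences on a pooled score were:

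- identical predictors: 0.02 or less
- mostly shared (HSA 0.35/0.35, non-HSA 0.25/0.35): 0.05
- partly shared (0.2/0.1 and 0.1/0.2): 0.10
- partly shared (0.35/0.175 and 0.175/0.35): 0.21
- separate drivers: about 0.2 at log-odds 0.2, 0.35-0.40 at 0.35, and 0.43-0.48 at 0.5

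Pooled differences stayed at about 0.01. In the separate-driver case, narrowing the caliper from 0.6 to 0.1 SD did not help: 0.228 became 0.195, 0.345 became 0.375, and 0.431 became 0.481.

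**HSA against non-HSA.** No calculation is needed. Matching each type to traditional members does nothing to bring the two types together, and neither C.6 nor C.9 has a step that does.

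**What an imbalance could do to an effect (illustration).** Suppose 1 SD of an unbalanced covariate, not otherwise adjusted for, shifts the change in adherence by 1 to 5 points. An imbalance of 0.1 SD then gives 0.1 to 0.5 points, and 0.5 SD gives 0.5 to 2.5 points. The example change in C.10 is 49% to 46%, or 3 points.

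**The case against.** A reader might infer that the HSA arm is in fact unbalanced. The documents do not show that. They give no covariates by HDHP type, and if the same factors predict both types the imbalance disappears. Some sharing is plausible, because C.8 reports that plan and out-of-pocket costs predict HDHP enrollment in general. The largest simulated values come from separate drivers, which is the extreme case. Neither simulation models the four employer strata or clustering by employer. All of this stands.

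A covariate difference is also not an effect bias. Difference-in-differences removes fixed level differences, and the Aim 1 segmented model fits the baseline trend. Matching on the baseline outcome and patient-level adjustment help further. This stands in part. What can remain is change after the switch that is linked to an unbalanced covariate. Baseline outcomes that enter through a pooled score share its limitation. The adjustments named in C.9 are at patient level for Aims 1 and 2, and the Aim 3 text names none. C.8 allows adjustment for employer covariates, but C.9 does not specify it. Since employees had no choice of plan, selection is mainly by employers.

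The planned three-cohort comparison could reveal a problem, so it would be wrong to say that the plan looks only at pooled balance. But it lists traditional controls as one group, does not specify each type against its own controls, and sets no threshold or remedy.

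**Conclusion.** The concern holds as a lack of assurance. The pooled score does not secure balance between HSA members and their own controls, and no design step balances HSA against non-HSA members or employers. C.1 promises only to reduce differences among employers choosing the three insurance types, but even that has no corresponding step for the two HDHP types.

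The possible HSA imbalance runs from about 0 to 0.5 SD under the assumed patterns. The true size depends on how far the predictors of the two plan types differ, which is not reported. An HSA-specific score brought it to 0.03 or less in every pattern tried. No bias in an effect has been demonstrated; the 0.1 to 2.5 points above rest on assumed slopes.

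A reader might also infer that the main HDHP-versus-traditional result is compromised. It is not: pooled balance was good throughout. The point concerns the estimates by type and the contrast between types. It should be fixed before those are produced.

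**What to change.** At employer and member level, replace the pooled score with two type-specific scores (HSA versus traditional, non-HSA versus traditional) or one three-category multinomial score. State the outcome of the member-level model explicitly. Match controls separately for each type.

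For the HSA versus non-HSA contrast, weight or match the two HDHP groups to a common distribution of the C.8 employer and member covariates and the baseline outcome. Separate matching alone would leave the two effects estimated in different populations.

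Report standardized differences for HSA versus its controls, non-HSA versus its controls, and HSA versus non-HSA. Set in advance the threshold that triggers action and the action to take, such as rematching or adjusting for the covariate, employer-level ones included.

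The cost is extra model and matching runs on data the plan says will be in-house. A few HSA members may go unmatched. Some controls may serve both types, which the variance for the contrast should reflect.
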